#### 5.1.1. Primary Endpoint(s)

The primary efficacy endpoint is the overall acute GVHD response at Day 28. The overall acute GVHD response is defined as improvement from Baseline in any organ (skin, lower GI tract and liver) by at least 1 stage, without progression in any other organ and with no additional therapy being administered. Baseline will be defined as the stage value determined at the diagnosis i.e. the first value recorded prior to 1st ALXN1007 infusion. At every visit, patients will be graded according to the Modified Keystone Grading Schema displayed in **Table 2**.

**Table 2. Modified Keystone Grading Schema**

	Stage 0	Stage 1	Stage 2	Stage 3	Stage 4
Skin	No Rash	Rash <25% BSA	Rash 25-50% BSA	Rash >50% BSA	Bullae and desquamation
Lower GI Tract	<500 ml/day stool volume	500-1000 ml/day stool volume OR Severe nausea and vomiting	1001-1500 ml/day stool volume	>1500 ml/day stool volume	Severe abdominal pain +/- ileus, frank blood or melena
Liver	Bilirubin ≤2 mg/dl	2.1-3 mg/dl	3.1-6 mg/dl	6.1-15 mg/dl	>15 mg/dl

Abbreviations: BSA = body surface area; GI = gastrointestinal

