6.1.1.2. GVHD Staging

Staging will be collected at all time points indicated in the Schedule of Events (including at Screening and Baseline; refer to Table 3 and Table 4). In addition, the stage at the time of diagnosis, that can occur up to 7 days prior of the first dose of ALXN1007, will also be recorded and will be used 1) to determine study eligibility and 2) for comparison to post-Baseline GVHD staging to assess treatment response to ALXN1007 in combination with corticosteroids. Acute GVHD staging will be performed using the Modified Keystone Grading Schema (Table 10 and Appendix 1), which includes skin, liver and lower GI assessments. Lower GI assessment consists of determination of stool volume over a 24-hour period. Detailed instructions for determining stool volume can be found in the study operations manual (SOM) for the study.

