7. SELECTION AND WITHDRAWAL OF SUBJECTS

7.1. Subject Inclusion Criteria

Only subjects meeting the following criteria are eligible for study participation.

- 1. Subjects must be males or females age 18 years or older.
- 2. Subjects with Stage 1-4 (per the Modified Keystone Grading Schema) acute GVHD of the lower GI tract, without signs of chronic GVHD, at the time of diagnosis, which developed in the first 180 days following allogeneic hematopoietic cell transplantation (HCT) using bone marrow, peripheral blood or cord blood; or after pre-planned donor lymphocyte infusion.
- 3. Subjects are willing to undergo or must have had an endoscopy of the upper and/or lower GI tract and biopsy to confirm GI GVHD within 7 days of screening. Biopsy results are not needed to initiate treatment; however, if GI GVHD is not confirmed histologically, treatment with ALXN1007 will be discontinued.
- 4. Subjects must be receiving systemic corticosteroids.
- 5. Subjects with an absolute neutrophil count (ANC) >500/µL at Screening.
- 6. Subjects and spouse/partner who are of childbearing potential must be using highly effective contraception consisting of 2 forms of birth control (at least 1 of which must be a barrier method) starting at Screening and continuing through the entire study (for at least 3 months after the last dose of ALXN1007 if study treatment is stopped early or subject withdraws consent). Highly effective contraception is defined as:
 - a. Established use of oral, injected or implanted hormonal methods of contraception.
 - b. Placement of an intrauterine device or intrauterine system.
 - c. Double barrier methods of contraception: condom or occlusive cap (diaphragm or cervical/vault caps) with spermicidal foam/gel/film/cream/suppository (double barrier method will count as 2 forms of contraception).
- 7. Male subjects must not donate sperm during the Screening and Treatment Periods, and for at least 3 months after the last dose of ALXN1007.
- 8. Subjects are willing and able to give written informed consent and to comply with all study visits and procedures.

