10. EFFICACY ASSESSMENTS

10.1. Primary Efficacy Assessment: Overall Acute GVHD Response

The primary efficacy assessment is overall acute GVHD response at Day 28. Overall acute GVHD response is defined as improvement from diagnosis in any organ by at least 1 stage, without progression in any other organ and with no additional therapy (-ies) being administered. At every visit, subjects will be graded according to the Modified Keystone Grading Schema displayed in Table 10 and Appendix 1.

 Table 10:
 Modified Keystone Grading Schema

	Stage 0	Stage 1	Stage 2	Stage 3	Stage 4
Skin	No Rash	Rash <25% BSA	25-50% BSA	>50% BSA	Bullae and
SKIII	140 Rusii	Rasii \23/0 DSA	23-30/0 DSA	≥3070 D3A	desquamation
Lower GI Tract ¹	<500 ml/day stool volume	500-1000 ml/day stool volume	1001-1500 ml/day stool volume	>1500 ml/ day stool volume	Severe abdominal pain +/- ileus, frank blood or melena
Liver ²	≤2 mg/dl	2.1-3 mg/dl	3.1-6 mg/dl	6.1-15 mg/dl	>15 mg/dl

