### **4.1. Changes from Analyses Specified in the Protocol**

Following changes in analyses specified in the protocol are noted:

- Safety analyses will be only performed on safety set as opposed to both safety set and modified safety set as mentioned in the protocol.
- Demographics, baseline characteristics and medical history will be only summarized for safety set as opposed to safety set, modified full analysis set and per-protocol set as mentioned in the protocol.
- The imputation rule has been modified from that described in the protocol for overall acute GVHD response, acute GI-GVHD response and acute GVHD response involving all organs.

In addition due to early termination of the study, an abbreviated CSR will be written and a number of pre-specified analyses will not be performed however by-patient listings will be generated for all data collected for this study.

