### **4.2. Changes from Analyses Specified in the Previous Version of the SAP**

See section 4.1.

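### SAP Table 2 defines lower GI Stage 1 more widely than the protocol, the primary endpoint is graded by that table, and the difference is not declared

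*SAP*

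**What the plan says.** The protocol prints the Modified Keystone schema in the synopsis, in Table 10 (Section 10.1) and in Appendix 1. In all three, lower GI Stage 1 is "500-1000 ml/day stool volume" and nothing else. Section 6.1.1.2 adds: "Lower GI assessment consists of determination of stool volume over a 24-hour period". The schema drives the primary endpoint: "Overall acute GVHD response is defined as improvement from diagnosis in any organ by at least 1 stage", with no progression in another organ and no additional therapy. It also drives eligibility, since inclusion criterion 2 admits "Subjects with Stage 1-4 (per the Modified Keystone Grading Schema) acute GVHD of the lower GI tract".

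SAP Table 2 carries the same title, but its lower GI Stage 1 cell reads "500-1000 ml/day stool volume OR Severe nausea and vomiting". SAP 5.1.1, which defines the primary endpoint, states: "At every visit, patients will be graded according to the Modified Keystone Grading Schema displayed in" Table 2.

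SAP 4.1 opens with "Following changes in analyses specified in the protocol are noted" and lists three items: the safety population, the population for baseline summaries, and the imputation rule. It then notes analyses dropped for the abbreviated report. The grading schema is not mentioned. SAP 4.2 says only "See section 4.1", and SAP Appendix 9.2 reports no changes.

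**The concern.** Two documents give different definitions of a stage under one name, and the primary endpoint is a change in that stage. Someone who reads the SAP's list of changes would conclude that the scale is the protocol's.

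The difference sits at the boundary between Stage 0 and Stage 1. For a subject enrolled at lower GI Stage 1, crossing that boundary is the only GI improvement possible. It is also the boundary that defines complete response in SAP 5.1.2.1 and 5.1.2.2. At stake are a small number of responder classifications in small cohorts, and agreement between the two documents on what a Day 28 response is.

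**Working it through.** The plan states no figure that depends on this point, so there is none to reproduce. The check compares the texts, follows one clinical picture through both scales, and sizes one reclassified subject.

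**1. The two scales, lower GI row**

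| Stage | Protocol Table 10 | SAP Table 2 |
|---|---|---|
| 0 | under 500 ml/day | same |
| 1 | 500 to 1000 ml/day | same range, or severe nausea and vomiting |
| 2 | 1001 to 1500 ml/day | same |
| 3 | over 1500 ml/day | same |
| 4 | defined by pain, ileus or bleeding | same |

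The skin and liver cut-offs also agree. One cell differs.

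**2. One subject under both scales**

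Take stool volume below 500 ml/day with severe nausea and vomiting at Day 28. The SAP has no rule for a subject who fits two cells, so I assume the higher stage applies. The Day 28 stage is then 0 under the protocol and 1 under the SAP. GI improvement means stage at diagnosis minus stage at Day 28 is at least 1.

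| Stage at diagnosis | Protocol | SAP | GI improved? | GI category* |
|---|---|---|---|---|
| 1 | 1 − 0 = 1 | 1 − 1 = 0 | yes / no | CR becomes NR |
| 2 | 2 − 0 = 2 | 2 − 1 = 1 | yes / yes | CR becomes PR |
| 3 | 3 − 0 = 3 | 3 − 1 = 2 | yes / yes | CR becomes PR |
| 4 | 4 − 0 = 4 | 4 − 1 = 3 | yes / yes | CR becomes PR |

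*By the SAP 5.1.2.1 categories, with no deterioration in another organ and no secondary therapy.

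Consequences for the primary endpoint:

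- Stage 1 at diagnosis: the outcome flips from response to non-response only if no other organ improves (otherwise the subject responds under both), no other organ progresses and no additional therapy is given (otherwise the subject fails under both).
- Stage 2 to 4 at diagnosis: the GI tract improves by at least one stage under both scales, so the primary outcome does not change. All-organ CR becomes PR if the other organs are at Stage 0.
- The same picture at diagnosis is Stage 0 under the protocol, which does not meet inclusion criterion 2, and Stage 1 under SAP Table 2.

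**3. Size of one flip**

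The shift is 1/n. Protocol Section 6.2 gives up to 36 subjects, at most 18 in Cohort 1 and about 6 at most in each other cohort. SAP Section 7 also tabulates the groups combined.

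- n = 6: 1/6 = 16.7 points
- n = 18: 1/18 = 5.6 points
- n = 36: 1/36 = 2.8 points

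The documents give no expected response rate. Assuming 50% purely for illustration, the Clopper-Pearson 95% intervals (the method in SAP 7.2.1) change as follows:

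| n | Before | After one flip |
|---|---|---|
| 6 | 3/6 = 50.0% (11.8 to 88.2) | 2/6 = 33.3% (4.3 to 77.7) |
| 18 | 9/18 = 50.0% (26.0 to 74.0) | 8/18 = 44.4% (21.5 to 69.2) |
| 36 | 18/36 = 50.0% (32.9 to 67.1) | 17/36 = 47.2% (30.4 to 64.5) |

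**The case against.** The strongest reply is that no subject need be reclassified. The protocol tells sites to stage by its own schema at each visit, and the SAP appears to work from recorded values. Its efficacy baseline is a recorded stage (5.1.1), the baseline table shows the staging score (7.1.3.2.3), individual scores and stool volumes are listed by patient (7.2.2.1.1), and the derived-variable specifications (9.4) contain no algorithm for building a stage from Table 2. If recorded protocol stages are analysed, the effect is nil. This largely stands as a limit on the consequence. It does not remove the point, because the SAP never names the source of the stage and its primary endpoint section directs the reader to the wider table.

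It is also fair to say that little rests on one cell: there is no hypothesis test, no sample-size or error-rate figure depends on it, and the study ended early with an abbreviated report.

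A reader might infer four stronger things, which the documents do not support:

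- That every reclassified subject moves the Day 28 rate. Step 2 of the working shows this fails for Stages 2 to 4, and for Stage 1 it needs further conditions.
- That an upper GI symptom has been put in a lower GI stage. Neither document says so; both list nausea and vomiting simply under gut in the criteria for very good partial response.
- That the criterion has no data source because the visit schedule has no nausea item. The schedule has a single staging row, and stool volume has no row of its own either. Nor is the stool-volume sentence in Section 6.1.1.2 exhaustive, since Stage 4 is defined by other signs. The operations manual is not available to check.
- That the sponsor deliberately changed the scale. The wording may have been carried over from another version: SAP 7.4 cites protocol Section 7.5.2 for the mortality rule, which is in Section 6.5.4 here.

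**Conclusion.** The mismatch is certain. The two documents define lower GI Stage 1 differently, the SAP ties the primary endpoint to its own version, and its list of changes omits the difference. That should be corrected, because the conflict lies in the definition of the primary endpoint.

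The effect on results is possible but not shown. It requires that stages were assigned or re-derived under SAP Table 2, and that at least one subject had low stool volume with severe nausea and vomiting at Day 28. The primary rate then moves only through subjects at Stage 1 at diagnosis who meet the further conditions in the working. For subjects eligible under the protocol, the added criterion can only raise a Day 28 stage from 0 to 1, so it can only lower the counts of responders and complete responders. The size is one subject's share of the group for each flip. The documents do not say how many subjects, if any, would be affected.

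**What to change.** Bring SAP Table 2 into line with protocol Table 10 by removing the added criterion. Add one sentence to SAP 5.1.1 stating that the stage recorded by the site under the protocol schema is the one analysed.

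Before doing so, confirm from the case report form and the operations manual which definition sites used. If it was the wider one, list the change in SAP 4.1 and report the Day 28 response on the protocol scale as the primary result where the data allow. The listed stool volumes should help to rebuild it.

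The cost is one table cell and one sentence. If the wider definition was used, it also takes one entry in SAP 4.1 and a restaging on the protocol scale, which is feasible only for subjects whose stool volumes were recorded.

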## 5.1.2. Other Efficacy Endpoints

### 5.1.2.1. Acute GI GVHD response

Acute GI-GVHD responses will be derived based on the following order (Progression, NR, MR, PR and CR) and these responses are mutually exclusive. The effect of secondary therapy only needs to be applied to 'NR' and no need to apply separately to MR, PR and CR because of inherent ordering.

- **Progression:** deterioration in lower GI tract staging (positive change from baseline).
- **No Response (NR):** no change in lower GI tract staging OR receiving secondary therapy.
- **Mixed Response (MR):** improvement in lower GI tract AND deterioration in another organ.
- **Partial Response (PR):** improvement in lower GI tract (provided lower GI tract staging is not 0) AND no deterioration in another organ.
- **Complete Response (CR):** lower GI tract Stage = 0

### 5.1.2.2. Response for All Organs Involved with Acute GVHD

Acute all organ-GVHD responses will be derived based on the following order (Progression, NR, MR, PR and CR) and these responses are mutually exclusive. Note, the effect of secondary therapy only needs to be applied to 'NR' and no need to apply separately to MR, PR and CR.

- **Progression:** Deterioration in at least 1 organ AND no improvement in other organs
- **No Response (NR):** no change in any organ OR receiving secondary therapy
- **Mixed Response (MR):** Improvement in at least 1 organ AND deterioration in another organ
- **Partial Response (PR):** Improvement in at least 1 organ AND no deterioration in another organ (provided not all stages are 0)
- **Complete Response (CR):** all organ stages are 0

### 5.1.2.3. Very Good Partial Response (VGPR):

- **Skin:** No rash, or residual erythematous rash involving <25% of the body surface, without bullae (residual faint erythema and hyperpigmentation do not count)
- **Liver:** Total serum bilirubin concentration <2 mg/dL or <25% of baseline at enrollment
- **Gut:**
  - Tolerating food or enteral feeding
  - Predominantly formed stools
  - No overt gastrointestinal bleeding or abdominal cramping

- No more than occasional nausea or vomiting

Note: For abbreviated CSR, this endpoint will not be analyzed.

#### 5.1.2.4. Treatment Failure

The proportion of treatment failures will be determined over time. The following will be considered as treatment failures:

- No response (all organs)
- Progression (all organs)
- Administration of additional systemic therapy for GVHD (or re-escalation of corticosteroid dose to  $\geq 2.5$  mg/kg/day of prednisone [or methylprednisolone equivalent of 2 mg/kg/day])
- Mortality occurred prior to Day 56

Note: For abbreviated CSR, this endpoint will not be analyzed.

#### 5.1.2.5. Acute GVHD Flares

Flares are defined as any progression of acute GVHD through Day 86 after an initial response (i.e., earlier CR or PR) that require re-escalation of corticosteroid dosing, or initiation of additional topical or systemic therapy for GVHD.

Note: For abbreviated CSR, this endpoint will not be analyzed.

#### 5.1.2.6. Discontinuation of Immunosuppressive Medications

Patients are expected to be on immunosuppressive medications at baseline and during the study (on or after 1st dose of ALXN1007). For analysis purpose, the immunosuppressive medications used for GVHD will be identified using Standardized Drug Grouping (SDG) classification based on WHO drug dictionary. The time (days) on immunosuppressive medications will be calculated as (last date on immunosuppressive medication – date of 1st ALXN1007 dose) + 1.

Note: For abbreviated CSR, this endpoint will not be summarized, however a by-patient listing will be produced.

#### 5.1.2.7. Cumulative and Average Corticosteroid Dose

Cumulative and average corticosteroid dose at Days 28, 56, 86 and 180 will be analyzed. For analysis purpose, the corticosteroids during the study will be identified using Standardized Drug Grouping (SDG) classification based on WHO drug dictionary. The prednisone equivalent of corticosteroid dose in mg will be calculated using the following conversion table using the dosing frequency and numeric dose as captured on the case report form:

**Table 3. Prednisone Equivalence Conversion**

Medication	Prednisone equivalent (mg)
Dexamethasone	6

Medication	Prednisone equivalent (mg)
Hydrocortisone	0.25
Hydrocortisone Sodium Succinate	0.25
Methylprednisolone	1.25
Methylprednisolone Sodium Succinate	1.25
Prednisone	1

Note: For abbreviated CSR, steroid dose will not be summarized, however a by-patient listing will be produced for all concomitant medications.

#### **5.1.2.8. Overall Survival**

Assessment of overall survival at Days 180 and 360 will be measured based on the time (days) since 1st ALXN1007 dose to death due to any reason. Patients with incomplete follow-up for other reasons will be censored.

#### **5.1.2.9. Non-Relapse Mortality**

Assessment of non-relapse mortality at days 180 and 360 will be measured based on the time (days) since 1st ALXN1007 dose to death due to any reason other than the underlying malignancy relapse. Relapse related deaths will be considered as competing risk. Patients with incomplete follow-up for any other reasons will be censored.

### **5.2. Safety**

The safety of ALXN1007 will be assessed based on incidence and severity of treatment-emergent adverse events (TEAEs), serious adverse events (SAEs), and changes from baseline through trial completion in vital signs, ECG, routine clinical laboratory tests (chemistry, hematology, urinalysis), incidence and titer of antibodies to ALXN1007, and pregnancy tests for female patients of childbearing potential.

Note: see details in the later sections for which parameters the results will not be summarized.

#### **5.2.1. Adverse Events (AEs)**

Treatment-emergent adverse events (TEAE) will be defined as any adverse event with onset on or after 1st ALXN1007 administration.

#### **5.2.2. Vital Signs**

Following vital signs are measured by visit for this study:

 
• Systolic blood pressure (mmHg)
 
• Diastolic blood pressure (mmHg)
 
	
 
• Respiration rate (RR)
 
• Weight (kg)
 

---	--

• Heart Rate (HR) (beats per minute)

• Temperature (°C)

	

• Height (cm), measured at screening only

---	---

### 5.2.3. Laboratory Assessments

Following laboratory parameters are collected for this study by visit:

- Chemistry panel,
- Coagulation panel,
- CBC with differential
- Platelets
- Urinalysis
- Stool test for *C. difficile*
- Blood test for absolute neutrophil count (ANC)
- Creatinine clearance
- Serum pregnancy test
- Urine dipstick pregnancy test
- Creatine phosphokinase (CPK)
- Thyroid function tests (TPO, TSH, FT-4)
- Levels of CSA, tacrolimus and/or sirolimus

### 5.2.4. Physical Examination

Abnormality finding for following body systems is collected for this study:

- General appearance
- Skin
- HEENT (Head, Ear, Eye, Nose, Throat)
- Neck
- Lymph nodes
- Chest
- Heart
- Abdomen
- Extremities
- Neurological
- Musculoskeletal

### 5.2.5. Electrocardiogram (ECG)

A 12-lead electrocardiogram (ECG) will be conducted to assess the ECG outcome as follows:

- Normal
- Abnormal
  - Clinically significant
  - Not clinically significant.

### **5.2.6. Immunogenicity**

Blood samples will be collected to test for antibodies to ALXN1007 in plasma just prior to dosing, at Baseline and on Days 7, 28, 56, 86 and 180, as well as at the ET visit. Blood samples will be evaluated for anti-drug antibodies (ADA) to describe the presence or absence of an immune response to ALXN1007 and to evaluate, if antibodies are detected, whether the antibodies neutralize the activity of ALXN1007 (ability of ALXN1007 to inhibit C5a). If tested positive on Day 180 or the ET visit, the test may be repeated on a 3-month basis until it is negative or stabilizes, based on the measured titer and the safety assessments in that specific patient.

Note: For abbreviated CSR, no summaries will be performed for antibodies, however all available results will be listed.

### **5.3. Pharmacokinetic and Pharmacodynamic Analysis**

Blood samples for PK/PD will be collected at the time points indicated in the schedule of events (Refer Table 3 in protocol) and plasma assayed for ALXN1007 concentration. The actual blood sampling times will be recorded and used in calculations for PK parameter estimation.

The PD effects of ALXN1007 will be determined by assessing plasma concentrations of biomarkers, which will include C3, C4, C5a, C5 and sC5b-9. Serum terminal complement activity will be measured by the cRBC hemolysis and Wieslab™ CCP assays.

The PK/PD modeling analyses will be detailed in a separate analysis plan.

Note: For abbreviated CSR, no analysis will be performed for PK and PD.

### **5.4. Exploratory Biomarker Assessment**

Blood samples will be collected just prior to dosing at Baseline, Days 7, 28, 49, 86 and 180, as well as the ET visit ; and may be used to characterize changes in the levels of biomarkers associated with alternative complement pathways activation or of mechanistic biomarkers thought to be associated with the development of GI GVHD. Biomarkers associated to complement may include, but are not limited to assessments of plasma Ba and Bb. Additional biomarkers associated with GVHD and downstream effects of complement activation may include, but are not limited to, tumor necrosis factor receptor 1 (TNFR1), suppressor of tumorigenicity 2 (ST2) and regenerating islet-derived protein 3 alpha (REG3a). Additional exploratory analyses, including anti-factor H antibody titer, may be performed.

Note: For abbreviated CSR, no analysis will be performed for exploratory biomarkers.

